2.2 Secondary endpoints

2.2.1 Secondary efficacy endpoints

- Responder for HbA1c after 26 weeks of treatment (Yes/No):
 - HbA1c < 7.0% (53 mmol/mol)*
 - HbA1c ≤ 6.5% (48 mmol/mol)*
 - HbA1c < 7.0% without weight gain*
 - HbA1c < 7.0% without treatment emergent severe or blood glucose (BG) confirmed symptomatic hypoglycaemic episodes*
- Change from baseline after 26 weeks of treatment in:
 - Self-Measured Blood Glucose (SMBG) 7-point profile

- 7-point profile (individual points in the profile)*
- Mean of 7-point profile*
- Mean of postprandial increments (from before meal to 90 min after for breakfast, lunch and dinner). The mean increment over all meals will be derived as the mean of all available meal increments.*
- Fasting plasma glucose (FPG)*
- Waist circumference*
- Body weight*
- Body mass index (BMI)*
- Blood pressure (systolic and diastolic)*
- Fasting C-peptide, fasting insulin, fasting glucagon, proinsulin, proinsulin/insulin, HOMA-B, HOMA-IR after 26 weeks of treatment*
- Fasting lipid profile (total cholesterol, low density lipoprotein cholesterol [LDL cholesterol], high density lipoprotein cholesterol [HDL cholesterol], very low density lipoprotein cholesterol [VLDL cholesterol], triglycerides, and free fatty acids) after 26 weeks of treatment*

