Unless otherwise specified, laboratory values below the lower limit of quantification (LLOQ) will be set to $\frac{1}{2}$ LLOQ.

For measurements over time, mean values will be plotted to explore the trajectory over time. LOCF imputed data will be used as the basis for plotting data, if not otherwise specified. For endpoints that are analysed log-transformed, the geometric mean values will be plotted.

An analysis of covariance (ANCOVA) model will be applied for the primary endpoint and continuous secondary endpoints after 26 weeks of treatment. The model includes treatment as a fixed effect and the corresponding baseline value as a covariate. In the following, this model will be referred to as the standard ANCOVA model.

Presentation of results from a statistical analysis will include the estimated mean treatment effects (Least Square Means [LSMeans]) for absolute values and change from baseline. In addition, estimated mean treatment difference (or ratio) will be presented together with the two-sided 95% confidence interval and corresponding two-sided p-value. The “obsmargins” option will be used in the “LSMEANS TREATMENT”.ⁱ

Handling of missing data

The expected percentage of missing data is around 10%. In accordance with industry guidanceⁱⁱ endpoints will be assessed at frequent visits and also on subjects who withdraw prematurely. This will facilitate an analysis in accordance with ITT principles. Also, the combined information on frequent outcomes and information on reason for drop-out is assumed to account for the missing data anticipated.

If not otherwise specified, the value from the randomisation visit (Visit 8) will be used as the baseline value. If the value measured at the randomisation visit is missing and the assessment has also been made at an earlier visit, then the non-missing value obtained at the preceding visit closest to Visit 8 will be used as the baseline value.

Missing values (including intermittent missing values) will be imputed using the LOCF method. Subjects without data after randomisation will be included by carrying forward their baseline value. In this trial, sensitivity analyses will be made to examine the robustness of the LOCF method.

Handling of laboratory measurements

A laboratory measurement in which the central laboratory could not guarantee a reliability of data, e.g. measurements with a comment like "Only for reference because of xxxx", will not be used for the summary and statistical analysis.

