3.1 Sample size calculation

Sample size calculations are described in the protocol section 17.1 and will not further be described here.

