3.3 Primary endpoint

The primary endpoint is the change from baseline in HbA1c after 26 weeks of treatment.

The change from baseline in HbA1c after 26 weeks of treatment will be analysed using an analysis of covariance (ANCOVA) model with treatment as a fixed effect and baseline HbA1c as a covariate.

Missing values after 26 weeks of treatment will be imputed applying last observation carried forward (LOCF) using HbA1c values at and after baseline.

Superiority of liraglutide 1.8 mg/day vs. liraglutide 0.9 mg/day will be considered as confirmed if the 95% confidence interval for the treatment difference (liraglutide 1.8 mg/day minus liraglutide 0.9 mg/day) for change from baseline in HbA1c lies entirely below 0.0%; equivalent to a one-sided test with significance level of 2.5%. Conclusion of superiority will be based on FAS.

Additionally, change from baseline in HbA1c after 52 weeks of treatment will be presented descriptively for the liraglutide 1.8 mg/day treatment arm.

Sensitivity analysis

Sensitivity analysis will be performed on FAS using the mixed model for repeated measurements (MMRM) method. All HbA1c values available post baseline at scheduled measurement times will be analysed in a linear mixed normal model using an unstructured residual covariance matrix for HbA1c measurements within the same subject. The model will include treatment and visit as fixed factors and baseline HbA1c as a covariate. Interactions between visit and treatment and between

visit and baseline HbA1c will also be included in the model. The results of sensitivity analyses will be compared to the result of the standard ANCOVA method using LOCF for imputation of missing data.

Further, a pattern mixture model approach using multiple imputation and mimicking an ITT scenario will be applied. Imputation in both arms will be based on liraglutide 0.9 mg/day values. The imputations will be done as follows:

- In the first step, for each subject with a non-monotone missing data pattern, missing values at visits prior to the last non-missing value for that subject are imputed using a Markov Chain Monte Carlo (MCMC) method (with seed of 20170427), in order to obtain a monotone missing data pattern. This imputation is done for each treatment group separately and 1000 copies of the dataset will be generated.

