- Mean of the 7-point profile, defined as the area under the profile (calculated using the trapezoidal method) divided by the measurement time. The area under the profile will be calculated for profiles which have at least one valid measurement. If a profile has only one valid measurement (e.g. 170 mg/dL before lunch), the value (i.e. 170 mg/dL) is set to the mean of 7-point profile.
- Mean of postprandial increments (from before meal to 90 min after for breakfast, lunch and dinner). The mean increment over all meals will be derived as the mean of all available meal increments. In case of only one valid increment (eg. 50 mg/dL for breakfast), the increment (i.e. 50 mg/dL) is set to the mean of postprandial increments.

A linear mixed effect model will be fitted to the 7-point SMBG profile data. The model will include treatment, time and interaction between treatment and time as fixed factors and subject as random effect. From the model mean profile by treatment and relevant treatment differences will be estimated and explored.

Change from baseline after 26 weeks of treatment in mean of the 7-point profile and post-prandial increment endpoints will be analysed separately using the standard ANCOVA model.

Blood pressure (systolic and diastolic)

Change from baseline in systolic blood pressure and diastolic blood pressure after 26 weeks of treatment will be analysed separately using the standard ANCOVA model.

Fasting C-peptide, fasting insulin, fasting glucagon, proinsulin, proinsulin/insulin, HOMA-B, HOMA-IR

In addition to fasting C-peptide, fasting insulin, fasting glucagon, and proinsulin, three derived parameters will be calculated; proinsulin/insulin ratio, beta-cell function (HOMA-B) and insulin resistance (HOMA-IR).

The calculation of the HOMA endpoints will be done as follows:

- Beta-cell function (%) = $20 \cdot \text{fasting insulin} [\mu\text{U/mL}] / (\text{FPG} [\text{mmol/L}] - 3.5)$
- Insulin resistance (%) = $\text{fasting insulin} [\mu\text{U/ml}] \cdot \text{FPG} [\text{mmol/l}] / 22.5$

These endpoints after 26 weeks of treatment will be analysed separately using the standard ANCOVA model. In these statistical analyses the endpoint will be log-transformed and so will the baseline covariate.

Fasting lipid profile

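### The SMBG profile model names only a random subject effect, so by default all seven points share one variance; if the true variances differ, the intervals for individual points have the wrong width

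*SAP*

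**What the plan says.** SAP section 3.4.1, under the SMBG 7-point profile, specifies a linear mixed model and describes its terms in one sentence: "The model will include treatment, time and interaction between treatment and time as fixed factors and subject as random effect". It names no residual covariance structure, no variance specific to a time point and no robust standard error. On the use of the model it says: "From the model mean profile by treatment and relevant treatment differences will be estimated and explored".

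Section 2.2.1 lists the individual points of the profile as a secondary efficacy endpoint. It carries the asterisk that section 2.2.2 explains as marking key secondary endpoints selected for disclosure. The general rule in section 3 on presenting statistical analyses is that the "estimated mean treatment difference (or ratio) will be presented together with the two-sided 95% confidence interval and corresponding two-sided p-value".

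For the other repeated-measures model in the plan, the HbA1c sensitivity analysis in section 3.3, the covariance is stated: a "linear mixed normal model using an unstructured residual covariance matrix for HbA1c measurements within the same subject".

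The mean of the profile and the mean postprandial increment do not depend on the profile model. Section 3.4.1 analyses each by the standard ANCOVA.

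**The concern.** The seven points are repeated measurements on the same subject within a day: before and 90 minutes after each of three meals, plus a seventh point that the SAP does not identify. A random subject intercept with independent, equal-variance residuals is compound symmetry, that is, one variance at every point and one correlation for every pair.

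Because the model includes treatment by time, the estimated difference at a point is, with complete data, simply the difference between the two arm means there. Its standard error is not specific to that point, because it uses a variance pooled over all seven. If some points are more variable than others, the reported interval is too short where variability is high and too long where it is low, and the p-values are off to match. At stake are the intervals and p-values for a disclosed endpoint, not the point estimates.

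**Working it through.** **Inputs.** From the SAP: the model terms (section 3.4.1), seven points of which three are pre-meal and three are 90 minutes post-meal (section 3.4.1), and two-sided 95% intervals (section 3). The SAP gives no SMBG SD, correlation or resulting standard error, so there is no figure of the plan's own to reproduce. The sample size is left to the protocol, but it cancels from the ratios below. Assumed: complete data, the same variances in both arms, pre-meal SD = 1, post-meal SD = r, and the seventh point grouped first with the pre-meal and then with the post-meal points. The SDs are those of whichever response is modelled. Section 2.2.1 speaks of change from baseline, whereas section 3.4.1 refers only to profile data.

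**Formulae.** Under the stated model with default residuals, the fitted variance at every point is the average of the seven true variances.

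- Width ratio at point t (model width / correct width) = sqrt(mean of the seven variances) / SD_t
- Coverage = 2Φ(1.96 × width ratio) − 1

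**Worked example, r = 1.3, seventh point grouped as pre-meal.** Mean variance = (4 × 1 + 3 × 1.69)/7 = 9.07/7 = 1.296, and its square root is 1.138.

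- Pre-meal: ratio 1.138/1 = 1.138, coverage 2Φ(2.23) − 1 = 97.4%
- Post-meal: ratio 1.138/1.3 = 0.876, coverage 2Φ(1.72) − 1 = 91.4%

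**Range.** Each cell gives width ratio and coverage.

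| r (assumed) | Pre-meal, 7th as pre | Post-meal, 7th as pre | Pre-meal, 7th as post | Post-meal, 7th as post |
|---|---|---|---|---|
| 0.8 | 0.920, 92.9% | 1.150, 97.6% | 0.891, 91.9% | 1.114, 97.1% |
| 1.0 | 1.000, 95.0% | 1.000, 95.0% | 1.000, 95.0% | 1.000, 95.0% |
| 1.1 | 1.044, 95.9% | 0.949, 93.7% | 1.058, 96.2% | 0.962, 94.1% |
| 1.2 | 1.090, 96.7% | 0.909, 92.5% | 1.119, 97.2% | 0.932, 93.2% |
| 1.3 | 1.138, 97.4% | 0.876, 91.4% | 1.181, 97.9% | 0.908, 92.5% |
| 1.5 | 1.239, 98.5% | 0.826, 89.5% | 1.309, 99.0% | 0.873, 91.3% |

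**Check by fitting the model.** The random-intercept model was fitted by REML to one simulated data set under each of two correlation patterns, with 150 subjects per arm (assumed), r = 1.3 and the seventh point grouped as pre-meal. The true standard errors are 1 × sqrt(2/150) = 0.115 pre-meal and 1.3 × sqrt(2/150) = 0.150 post-meal. The fitted standard error was the same at all seven points: 0.1298 under a correlation decaying as 0.8 per step and 0.1302 under a constant correlation of 0.5. The formula gives sqrt(1.296 × 2/150) = 0.131.

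The two patterns gave practically the same answer. With complete data the single-point intervals therefore depend on unequal variances, not on the correlation. The equal-correlation restriction matters for contrasts between points, or when points are missing.

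**The case against.** The strongest objection is that the plan shows no error as it stands. The SAP gives no SMBG variances and nowhere says that post-meal values vary more. At equal SDs the model is exact for single points. A reader might infer that the intervals are too wide before meals and too narrow after them, with type I error inflated after meals. The document does not support this: that direction needs the assumption r > 1, and at r = 0.8 it is reversed. Nor is every point's interval necessarily wrong, since a point whose SD is close to the pooled value is hardly affected. This objection stands, and the point is therefore put conditionally.

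Second, the SAP does not impose compound symmetry in words. It is silent on the residual covariance, so this is a gap with a restrictive default. That also stands. But the sentence describes the terms of the model, and an analyst who follows it literally will fit the default.

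Third, a reader might take the "using an unstructured residual covariance matrix for HbA1c measurements within the same subject" in section 3.3 as evidence that the plan contradicts itself. It does not: that model covers HbA1c across visits and serves as a sensitivity analysis for missing data. It shows only that the plan states a covariance structure elsewhere.

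Fourth, the consequences are limited. Differences from the profile model are to be explored, superiority rests on HbA1c alone, the mean and increment endpoints have their own ANCOVAs, and the asterisk denotes disclosure rather than confirmatory testing. If the general LOCF rule in section 3 also fills missing profile points, the missing-data route for the correlation restriction largely closes too. All this lowers the severity. It does not make equal variances a safe default. Since post = pre + increment, equal pre-meal and post-meal variances require the covariance of pre-meal value and increment to be exactly minus half the variance of the increment, and nothing in the SAP supports that.

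**Conclusion.** The point holds in conditional form. The only within-subject structure named for the SMBG profile model is a random subject effect. With default residuals, this gives every point a standard error based on the average variance. If variances differ between points, intervals and p-values are too optimistic at the more variable points and too conservative at the less variable ones.

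Size and direction cannot be determined from the SAP. Over assumed post/pre SD ratios of 1.1 to 1.5, post-meal coverage runs from 94.1% down to 89.5% and pre-meal coverage from 95.9% up to 99.0%, depending also on how the seventh point is grouped. These figures assume complete data and equal variances in the two arms.

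Severity is low: the endpoint is secondary and exploratory, and no confirmatory conclusion uses this model. The change is worth making because it is cheap and gives intervals of about the right width for a disclosed endpoint whatever the variances turn out to be.

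**What to change.** In SAP section 3.4.1, replace the random subject effect in the profile model with an unstructured residual covariance matrix for the seven points within a subject (in SAS: REPEATED time / SUBJECT=subject TYPE=UN). Name heterogeneous compound symmetry (TYPE=CSH) as the fallback if the model does not converge; it still gives each point its own variance. With time-specific variances the width ratio is 1.00 and coverage is about 95% at every point, whatever the SD ratio.

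The cost is a sentence or two of SAP text and a line of code, with no new data. The statistical price is 7 × 8/2 = 28 covariance parameters instead of 2 (subject and residual variance), hence the need for a fallback. With complete data the estimated differences at individual points do not change, only their standard errors.

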3.4.2 Safety endpoints

Adverse events

AEs will be coded using the most recent version of the Medical Dictionary for Regulatory Activities.

A treatment emergent adverse event (TEAE) is defined as an event that has onset date on or after the first day of IMP administration and no later than seven days after the last day on IMP. If the event has onset date before the first day of IMP administration and increases in severity during the treatment period and until 7 days after the last drug date, then this event should also be considered as a TEAE. Here the first day of IMP administration is defined as the first day of exposure to liraglutide.

AEs will be summarised descriptively for each of the following periods separately:

- The run-in period: TEAEs with an onset date on or after the first day of exposure to liraglutide and before the date of randomisation will be reported as part of the run-in period. For the run-in failure subjects, AEs with an onset date on or after the first day of exposure to liraglutide and no later than seven days after the last day of liraglutide treatment will be reported as part of the run-in period.
- The 26 week treatment period: TEAEs with an onset date on or after the date of randomisation and no later than seven days after Visit 16 (EOT26) will be reported as during 26 weeks of treatment. For subjects in the liraglutide 0.9 mg arm as well as for subjects in both arms who withdrew from the trial during 26 weeks of treatment, TEAEs with an onset date on or after the date of randomisation and no later than seven days after the last day of liraglutide treatment will be reported as part of 26 weeks of treatment.
- The 52 week treatment period: For the liraglutide 1.8 mg arm all TEAEs with an onset date on or after the date of randomisation will be reported as during 52 weeks of treatment.

For each of the above periods, AE data will be displayed in terms of the number of subjects with at least one event (N), the percentage of subjects with at least one event (%), the number of events (E) and the event rate per 100 years of exposure (R).

Summaries of AEs and of serious AEs will be presented as an overview including all AEs, serious AEs, number of deaths, AEs by severity, AEs by relation to treatment and AEs of special interest including AEs leading to withdrawal for each period.

Furthermore separate summary tables for each period will be presented based on system organ class and preferred terms for:

- All AEs
- Serious AEs
- Possibly or probably related AEs
- Severe, moderate and mild AEs
- AEs reported by safety areas of interest
- AEs with preferred term that are experienced by at least 5% of the subjects in any treatment arm or by at least 5% of all subjects

A listing for non-treatment emergent adverse events with onset date before the first day of exposure to liraglutide will be presented. A listing will also be presented for non-treatment emergent adverse events collected after the treatment emergent period according to the definition of TEAE.

Classification of Hypoglycaemia:

Treatment emergent: hypoglycaemic episodes will be defined as treatment emergent if the onset of the episode occurs on or after the first day of IMP administration, and no later than 7 days after the last day on IMP. Here the first day of IMP administration is defined as the first day of exposure to liraglutide.

Nocturnal hypoglycaemic episodes: are episodes occurring between 00:01 and 05.59 both inclusive.

[figure not shown]
Hypoglycaemic episodes are classified according to the Novo Nordisk classification of hypoglycaemia (see [Figure 3-1](#)) and the ADA classification of hypoglycaemia (see [Figure 3-2](#)).

Novo Nordisk classification of hypoglycaemia

In normal physiology, symptoms of hypoglycaemia occur below a plasma glucose level of 3.1 mmol/L (56 mg/dL)^{viii}. Therefore, Novo Nordisk has included hypoglycaemia with plasma glucose levels below this cut-off point in the definition of blood glucose (BG) confirmed hypoglycaemia.

Novo Nordisk uses the following classification (see [Figure 3-1](#)) in addition to the ADA classification:

Severe or BG confirmed symptomatic hypoglycaemia: An episode that is severe according to the ADA classification^{ix} or BG confirmed by a plasma glucose value <3.1 mmol/L (56 mg/dL) **with** symptoms consistent with hypoglycaemia.

[figure not shown]

Note: Glucose measurements are performed with capillary blood calibrated to plasma equivalent glucose values

Figure 3-1 Novo Nordisk classification of hypoglycaemia

ADA classification^{ix} of hypoglycaemia

- Severe hypoglycaemia: An episode requiring assistance of another person to actively administer carbohydrate, glucagon, or take other corrective actions. Plasma glucose concentrations may not be available during an event, but neurological recovery following the return of plasma glucose to normal is considered sufficient evidence that the event was induced by a low plasma glucose concentration.
- Asymptomatic hypoglycaemia: An episode not accompanied by typical symptoms of hypoglycaemia, but with a measured plasma glucose concentration ≤ 3.9 mmol/L (70 mg/dL).
- Documented symptomatic hypoglycaemia: An episode during which typical symptoms of hypoglycaemia are accompanied by a measured plasma glucose concentration ≤ 3.9 mmol/L (70 mg/dL).
- Pseudo-hypoglycaemia: An episode during which the person with diabetes reports any of the typical symptoms of hypoglycaemia with a measured plasma glucose concentration > 3.9 mmol/L (70 mg/dL) but approaching that level.
- Probable symptomatic hypoglycaemia: An episode during which symptoms of hypoglycaemia are not accompanied by a plasma glucose determination but that was presumably caused by a plasma glucose concentration ≤ 3.9 mmol/L (70 mg/dL).

Note: Glucose measurements are performed with capillary blood calibrated to plasma equivalent glucose values

Figure 3-2 ADA classification of hypoglycaemia

Hypoglycaemic episodes will be summarised descriptively for each of the following periods separately:

- The run-in period: Treatment emergent hypoglycaemic episodes where the onset date of the episode occurs on or after the first day of exposure to liraglutide and before the date of randomisation will be reported as part of the run-in period. For the run-in failure subjects, hypoglycaemic episodes where the onset date of the episode occurs on or after the first day of exposure to liraglutide and no later than seven days after the last day of liraglutide treatment will be reported as part of the run-in period.
- The 26 week treatment period: Treatment emergent hypoglycaemic episodes where the onset date of the episode occurs on or after the date of randomisation and no later than seven days after Visit 16 (EOT26) will be reported as during 26 weeks of treatment. For subjects in the liraglutide 0.9 mg arm as well as for subjects in both arms who withdrew from the trial during 26 weeks of treatment, treatment emergent hypoglycaemic episodes with an onset date on or after the date of randomisation and no later than seven days after the last day of liraglutide treatment will be reported as part of 26 weeks of treatment.
- The 52 week treatment period: For the liraglutide 1.8 mg arm all treatment emergent hypoglycaemic episodes with an onset date on or after the date of randomisation will be reported as during 52 weeks of treatment.

For each of the periods listed above, data on hypoglycaemic episodes are presented above in terms of the number of subjects with at least one event (N), the percentage of subjects with at least one event (%), the number of events (E) and the event rate per 100 years (R). Separate summaries are made for severe or BG confirmed symptomatic hypoglycaemic episodes, nocturnal severe or BG confirmed symptomatic hypoglycaemic episodes and the ADA classification of hypoglycaemia.

The number of hypoglycaemic episodes during 26 weeks of treatment will be analysed separately for each endpoint listed above using a negative binominal regression model with a log-link function and the logarithm of the time period in which a hypoglycaemic episode is considered to be part of the 26 week treatment period as offset. The model will include treatment as factor. For each endpoint, the analysis will be performed only if the number of episodes observed is adequate for convergence of the model fit.

Pulse

Pulse will be summarized descriptively.

Clinical evaluations (physical examination, eye examination and ECG)

Eye examination (fundoscopy/fundus photography) and ECG findings will be summarised descriptively, including:

- summaries for each visit
- shift table from baseline to after 26 weeks of treatment and after 52 weeks of treatment

Any findings in the physical examination evaluation at screening will be presented as listings. Any clinically significant deterioration of a pre-existing condition after the screening visit, as well as any new clinically significant findings will be recorded as adverse events.

Laboratory assessments

All laboratory parameters will be summarised descriptively.

The following tables will be presented based on both observed and LOCF imputed data:

- Shift tables from baseline to after 26 weeks of treatment and after 52 weeks of treatment
- Proportion of subjects with measurements outside reference range by treatment and week.

Laboratory values will be presented graphically as box plots by treatment and week.

For each laboratory parameter, individual values outside the reference ranges (abnormal values) will be listed.

For lipase and amylase the following rule will apply in the evaluation of the result:

- If the amylase or lipase baseline (at screening) value is $> 3 \times \text{UNR}$ this information is to be recorded as medical history for that subject.

The purpose of the calcitonin analysis is to evaluate longitudinal changes in calcitonin, with main focus on subjects who develop persistently high levels of calcitonin during the trial.

Calcitonin will be displayed in terms of the number of subjects (N), the percentage of subjects (%) and the incidence rate per 100 years of exposure (R). The following criteria are defined for tabulations:

Persistent (all post baseline measurements)

- From $< \text{UNR}$ to persistently $\geq \text{UNR}$
- From $< \text{UNR}$ to persistently $\geq 1.5 \text{ UNR}$
- From $< \text{UNR}$ to persistently $\geq 20 \text{ ng/L}$
- From $< \text{UNR}$ to persistently $\geq 50 \text{ ng/L}$
- From $< 20 \text{ ng/L}$ to persistently $\geq 20 \text{ ng/L}$
- From $< 50 \text{ ng/L}$ to persistently $\geq 50 \text{ ng/L}$

Incidental (at least one post baseline measurements)

- From $< \text{UNR}$ to $\geq \text{UNR}$
- From $< \text{UNR}$ to $\geq 1.5 \text{ UNR}$
- From $< \text{UNR}$ to $\geq 20 \text{ ng/L}$
- From $< \text{UNR}$ to $\geq 50 \text{ ng/L}$
- From $< 20 \text{ ng/L}$ to $\geq 20 \text{ ng/L}$
- From $< 50 \text{ ng/L}$ to $\geq 50 \text{ ng/L}$

The distribution of all calcitonin measurements across treatment groups and time will be shown with histograms and corresponding cumulative plots for actual levels of calcitonin and change from baseline. The plots will be presented by treatment group (using EOT measurement - LOCF) and within treatment group by week. Plots will be done by gender.

Summaries tables of calcitonin continuous measurements, will include number and percentage of observations $<$ and \geq LLOQ, minimum, Q25, median, Q75 and maximum. Summaries will be presented for all subjects and by gender.

Longitudinal changes for subjects with calcitonin levels $\geq 20 \text{ ng/L}$ will be plotted (longitudinal plots). The plots will be done by treatment and gender. They will be done for subjects in the persistent and incidental categories, separately.

A listing of subjects with at least one post baseline value $\geq 20 \text{ ng/L}$ will be done. The listing will include age, gender, calcitonin measurements over time and AE history (including preferred term, onset and stop dates).

4 Changes to the statistical analyses planned in the protocol

The following changes from the protocol are implemented in this SAP.

Full analysis set

In the protocol, it was stated that “In exceptional cases, subjects may be eliminated from the full analysis set. In such cases the elimination will be justified and documented.”. Since it is technically difficult to keep the statisticians and programmers blinded before database lock in this trial design, it is deleted in order to minimise the potential bias by excluding the subjects based on the knowledge of randomised treatment for each subject.

Data handling

The possible data handlings are described in order to minimise the potential bias and the following text in section 17.2 in the protocol section was deleted.

Before data are released for statistical analysis, a review of all data will take place to identify protocol deviations that could potentially affect the results. Any decision to exclude any subject or observation from the statistical analysis is the joint responsibility of the members of the study group. The subjects or observations to be excluded, and the reasons for their exclusion must be documented and signed by those responsible before database lock. The subjects and observations excluded from analysis sets, and the reason for this, will be described in the clinical trial report.

The following changes from SAP version 1 are implemented in SAP version 2.

Endpoints section is created according to the protocol and endpoints selected for disclosure are updated.

Sensitivity analysis

As a sensitivity analysis for the primary endpoint, a pattern mixture model approach using multiple imputation is added.

Blood pressure (systolic and diastolic)

Statistical analysis is added for change from baseline in systolic blood pressure and diastolic blood pressure after 26 weeks of treatment as well as other efficacy secondary endpoints.

Safety analysis set

In the protocol, it was stated that the Safety Analysis Set “includes all subjects receiving at least one dose of randomised treatment”. In order to clarify that all adverse events occurring after initiation of treatment with liraglutide (including during the run-in phase) will be reported appropriately, this has been updated to state “includes all subjects receiving at least one dose of liraglutide”. Deletions are ~~struck through~~ and new text is in **bold**.

- Safety Analysis Set (SAS): includes all subjects receiving at least one dose of ~~randomised treatment~~**liraglutide**. Subjects in the safety analysis set will contribute to the evaluation “as treated”.

~~Randomised~~ Subjects who are lost to follow up and where no exposure information of ~~the investigational product or comparators~~**liraglutide** is available ~~after randomisation~~ will be handled as unexposed.

Adverse events

In order to ensure proper alignment with the updated SAS definition, the definition of treatment emergent and the specification of AEs included in summary tables in each period are updated as follows. Deletions are ~~striketrough~~ and new text is in **bold**.

A treatment emergent adverse event (TEAE) is defined as an event that has onset date on or after the first day of IMP administration and no later than seven days after the last day on IMP. If the event has onset date before the first day of IMP administration and increases in severity during the treatment period and until 7 days after the last drug date, then this event should also be considered as a TEAE. Here the first day of IMP administration is defined as the first day of exposure to ~~randomised treatment~~**liraglutide**.

AEs will be summarised descriptively for each of the following periods separately:

- The run-in period: **TEAEs with an onset date on or after ~~Visit 2~~the first day of exposure to liraglutide and before the first day of exposure to randomised treatmentthe date of randomisation** will be reported as part of the run-in period. **For the run-in failure subjects, TEAEs with an onset date on or after the first day of exposure to liraglutide and no later than seven days after the last day of liraglutide treatment will be reported as part of the run-in period.**
- The 26 week treatment period: TEAEs with an onset date on or after ~~the first day of exposure to randomised treatment~~**the date of randomisation** and no later than seven days after Visit 16 (EOT26) will be reported as during 26 weeks of treatment. **For subjects in the liraglutide 0.9 mg arm as well as for subjects in both arm who withdrew from the trial during 26 weeks of treatment, TEAEs with an onset date on or after the date of randomisation and no later than seven days after the last day of liraglutide treatment will be reported as part of 26 weeks of treatment.**
- The 52 week treatment period: For the liraglutide 1.8 mg/day arm all TEAEs **with an onset date on or after the date of randomisation** will be reported as during 52 weeks of treatment.

A listing for non-treatment emergent adverse events with onset date before ~~Visit 2~~**the first day of exposure to liraglutide** will be presented. A listing will also be presented for non-treatment emergent adverse events collected after the treatment emergent period according to the definition of TEAE.

Hypoglycaemic episodes

In order to ensure proper alignment with the updated SAS definition, the definition of treatment emergent and the specification of hypoglycaemic episodes included in summary tables in each period are updated as follows. Deletions are ~~striketrough~~ and new text is in **bold**.

Treatment emergent: hypoglycaemic episodes will be defined as treatment emergent if the onset of the episode occurs on or after the first day of IMP administration, and no later than 7 days after the last day on IMP. Here the first day of IMP administration is defined as the first day of exposure to ~~randomised treatment~~ **liraglutide**.

Hypoglycaemic episodes will be summarised descriptively for each of the following periods separately:

- The run-in period: **Treatment emergent** hypoglycaemic episodes where the onset date of the episode occurs on or after ~~Visit 2~~ **the first day of exposure to liraglutide** and before ~~the first day of exposure to randomised treatment~~ **the date of randomisation** will be reported as part of the run-in period. **For the run-in failure subjects, hypoglycaemic episodes where the onset date of the episode occurs on or after the first day of exposure to liraglutide and no later than seven days after the last day of liraglutide treatment will be reported as part of the run-in period.**
- The 26 week treatment period: Treatment emergent hypoglycaemic episodes where the onset date of the episode occurs on or after ~~the first day of exposure to randomised treatment~~ **the date of randomisation** and no later than seven days after Visit 16 (EOT26) will be reported as during 26 weeks of treatment. **For subjects in the liraglutide 0.9 mg arm as well as for subjects in both arms who withdrew from the trial during 26 weeks of treatment, treatment emergent hypoglycaemic episodes with an onset date on or after the date of randomisation and no later than seven days after the last day of liraglutide treatment will be reported as part of 26 weeks of treatment.**
